### **17.3 Pilot work**

Pilot searches of the clinical dataset for the mental health service (CRIS system), since its year of inception in 2006 to the end of 2016, indicate that there are CORE-OM outcome data on more than 3,000 women who have been raped or have experienced other forms of sexual assault. From this we estimate around 300 women per year receiving psychological treatment who have a document of sexual assault on the CRIS system, therefore approximately 900 cases for 2016 to 2019.

We have already been in discussions with the Kent SARC staff, two of whom are our collaborators ([name] and [name]) and they have confirmed that they are able to provide us with an anonymized clinical dataset for the purposes of this study; the SARC service already has in place permission agreements from service users to the sharing of their anonymized data for research purposes. Pilot searches of the referral rates with the Kent SARC indicate that around 4-6 referrals per week are referred to the psychological treatment pathway per week (approximately 16-20 a month); before- and after-treatment assessment are taken for everyone in treatment. In 2016, the Kent SARC established the central database system for the reporting of clinical data of service users and, therefore, cases can be analysed from this date.

### **17.4 Permissions**

For analysis of the CRIS data, ethical approval will need to be obtained from the CRIS database oversight committee. For analysis of the Kent SARC data, relevant ethical approvals will be sought.

### **17.5 Analysis**

All analyses will be conducted in STATA version 14 (23). Descriptive statistics – proportional for categorical variables and means and standard deviations for quantitative variables – will be calculated to describe the sociodemographic and clinical characteristics of the sample. Main statistical analyses

will examine changes in psychological well-being (based on CORE outcome assessments before and after treatment) following psychological treatment from a mainstream mental health service compared to a SARC. We will examine the socio-demographic and clinical characteristics of the cohorts to explore whether there are systematic differences e.g. history of previous psychiatric contact such as admission. We will then address these using appropriate statistical techniques. We will stratify by gender and seek to match cases on socio-demographics such as ethnicity.

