### **17.2 Study design**

A retrospective cohort study using anonymised data

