### *Clinical Dataset SARC service*

The Kent SARC provides the only bespoke psychological therapies service in partnership with the local mental health NHS Trust and two third-sector organizations [Family Matters and East Kent Rاپeline]. The SARC treatment model utilizes specialist third-sector organizations, which offer counselling, alongside an NHS psychological therapy service. The third-sector organizations provide an alternative therapeutic model to the mainstream mental health model of SLaM, through the provision of specialist trauma-focused counselling for males and females reporting sexual assault via the Kent SARC. The SARC service and its partners have established a central database system for the reporting of clinical data of service users. The database includes detailed demographic and clinical information, including before- and after-therapy CORE Outcome Measure (CORE-OM) scores. The

research team will work with the SARC providers ([name] and [name]) to generate an anonymized clinical dataset of key demographic and clinical information and CORE outcome assessments for the purposes of this study.

Cases from each dataset will be matched on key clinical and demographic information, including age, gender, ethnicity and timing of assault (i.e. recent vs. non-recent).

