### **17.6 Health Economics**

We will assess the feasibility of comparing the cost of mental health care treatment for patients receiving treatment from mainstream mental health services compared to a SARC. Mental health resource use for patients attending traditional mental health services will be obtained from CRIS and costed using nationally published sources. The cost of the SARC will be calculated from the Kent SARC data, information collected from WP4 and the analysis conducted as part of WP3. We will conduct a cost-consequences analysis, reporting costs alongside outcomes for the two service types along with 95% confidence intervals to allow for evaluation of significant differences between the two service types. We will ensure the information reported is useful to policy makers and commissioners service planning and delivery through ongoing dialogue with key stakeholders.

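### WP5 compares before-to-after CORE change between two non-randomised services but does not commit to matching on or adjusting for the pre-treatment CORE-OM score, which both datasets hold

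*Protocol*

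**What the plan says.** Section 17.2 of the Protocol gives the WP5 design as "A retrospective cohort study using anonymised data". Section 17.5 states that the main analyses "will examine changes in psychological well-being (based on CORE outcome assessments before and after treatment", and that the contrast is the change "following psychological treatment from a mainstream mental health service compared to a SARC".

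Matching is described twice. Under the SARC dataset in 17.2: "Cases from each dataset will be matched on key clinical and demographic information, including age, gender, ethnicity and timing of assault". In 17.5: "We will stratify by gender and seek to match cases on socio-demographics such as ethnicity".

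Section 17.5 also provides for imbalance. It says "We will examine the socio-demographic and clinical characteristics of the cohorts to explore whether there are systematic differences", gives earlier psychiatric admission as an example, and continues: "We will then address these using appropriate statistical techniques".

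The pre-treatment score is available in both arms. Under 17.2, CRIS cases are identified partly by having CORE-OM recorded before and after therapy, and the SARC database is described as holding both scores. Section 17.3 adds that the SARC service takes both assessments for everyone in treatment. Nowhere in WP5 is the pre-treatment score named as a matching variable or covariate.

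**The concern.** The two arms come from different places. CRIS covers secondary care, substance misuse services and IAPT. The other arm is a SARC pathway combining third-sector trauma counselling with an NHS psychological therapy service. Section 12.1 describes referral to secondary care when need exceeds what IAPT can support, which tends to sort people by severity. Starting scores may therefore differ, and 17.5 itself anticipates systematic differences between the cohorts.

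When the outcome is change from a starting value, a difference in starting values can carry straight into the result. A group that enters treatment at a more extreme point tends to move back further, and that extra movement can be read as a better service. Matching on age, gender, ethnicity and timing of assault removes it only as far as those variables account for starting severity.

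At stake is the answer to research question 6 and objective 7, the outcome comparison between the bespoke SARC service and mainstream care. A larger sample does not help: it narrows the interval around a biased estimate.

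**Working it through.** **The plan's own figures.** WP5 states no sample size calculation, effect size, SD or pre-post correlation, so there is no result to reproduce. The only count is feasibility: 3,000 cases over about 10 years is 300 a year, and 300 x 3 = 900 for 2016 to 2019. It reproduces.

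**Inputs for the illustration**
- D, the baseline gap between services in SD units: assumed 0.2 to 0.5.
- r, the pre-post correlation: assumed 0.4 to 0.7.
- Group sizes: 900 from 17.3 for CRIS; for the SARC, 16 a month (the lower figure in 17.3) x 36 months = 576, which assumes three years and counts referrals. Both are likely too high once matching and completion of treatment are allowed for.

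**Bias of unadjusted change.** Take equal variances before and after, no true service effect, and one regression line common to both groups. The after-treatment gap is r x D, so the difference in mean change has size D - rD = (1 - r) x D. At D = 0.3 and r = 0.5 this is 0.5 x 0.3 = 0.15 SD.

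**Chance of nominal significance (two-sided 5%).** The SD of a change score is sqrt(2(1 - r)), which is 1.00 at r = 0.5. The standard error is 1.00 x sqrt(1/900 + 1/576) = 0.0534. Then 0.15 / 0.0534 = 2.81, giving a rejection probability of about 80%.

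Spurious difference in SD, with rejection probability in brackets:

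| D | r = 0.4 | r = 0.5 | r = 0.6 | r = 0.7 |
|---|---|---|---|---|
| 0.2 | 0.12 (54%) | 0.10 (47%) | 0.08 (39%) | 0.06 (31%) |
| 0.3 | 0.18 (87%) | 0.15 (80%) | 0.12 (71%) | 0.09 (59%) |
| 0.5 | 0.30 (99.9%) | 0.25 (99.7%) | 0.20 (98.7%) | 0.15 (95%) |

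**Precision.** Per-person residual variance is 2(1 - r) for change and 1 - r² with baseline adjustment. At r = 0.5 these are 1.00 and 0.75.

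**Does adjustment always cure it?** A simulation of 500 runs with D = 0.5, r = 0.5 and no true effect compared both analyses under two mechanisms:
- A, groups differ at baseline and share one regression line: change score biased by -0.25 SD, baseline-adjusted model by about 0.00.
- B, groups have stable, different true levels: change score biased by about 0.00, baseline-adjusted model by +0.25 SD.

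The two analyses differ by (1 - 0.5) x 0.5 = 0.25 SD in either case. Which one is right depends on an assumption the protocol does not state.

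**The case against.** The strongest reply is that the protocol excludes nothing. The list in 17.2 is open: it speaks of clinical as well as demographic information, and the four variables follow the word including. Section 17.5 undertakes to examine clinical characteristics and deal with systematic differences, and a pre-treatment CORE-OM score is a clinical characteristic. Covariate lists and model forms usually sit in a statistical analysis plan, which is not shown here. This stands to the extent that a reader should not infer that WP5 has ruled out baseline adjustment, that 17.5 confines itself to socio-demographics, or that earlier admission has been overlooked; 17.5 names it.

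It does not dispose of the point. The protocol has itself chosen change as the main contrast and has named variables in two places without the one most directly tied to that contrast. The two places also differ: 17.2 says cases will be matched, on clinical and demographic data; 17.5 says the team will seek to match, on socio-demographics. The fallback, "We will then address these using appropriate statistical techniques", follows inspection of the cohorts, so the choice between two analyses that can differ materially is made after the data have been seen.

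A second reply is that adjustment may itself mislead. Mechanism B is a live possibility with two such different source populations, and matching on a noisy baseline has the same weakness. That stands, and it is a reason to declare the assumption in advance and report both analyses.

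A reader might also infer a fault in the cost comparison, where 17.6 promises "95% confidence intervals to allow for evaluation of significant differences between the two service types". The text states no rule of comparing two separate intervals for overlap, and the intervals may equally be for the difference. No error can be shown there.

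**Conclusion.** The point holds in a limited form. WP5's main analysis rests on change in CORE between non-randomised services, and nothing in 17.2 or 17.5 commits to handling the pre-treatment score. If starting severity differs and both groups regress to a common line, unadjusted change is biased by (1 - r) x D: 0.06 to 0.30 SD over the assumed ranges, and 0.15 SD at D = 0.3 and r = 0.5. The actual size cannot be determined, because the protocol gives neither D nor r, and it would be zero if the services start level.

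The stronger statement, that WP5 will certainly report regression to the mean as a service effect, is not supported. The wording leaves room for adjustment, and the bias depends on the common-line assumption. What is supported is that the handling of the starting score should be fixed before outcomes are examined. This is a cheap improvement to a stated analysis that goes beyond filling in missing detail.

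**What to change.** - In 17.2 and 17.5, name pre-treatment CORE-OM in the matching or propensity set, and reconcile the two matching statements so that one list and one level of commitment applies.
- Make the main model after-treatment CORE-OM regressed on service, adjusted for pre-treatment CORE-OM and the matching variables.
- State the assumption this makes: given the starting score and the other covariates, the two groups would follow the same line if the services were equally effective.
- Report the change-score comparison as a sensitivity analysis, in the cohort matched or weighted on the other variables only. Once groups are matched on the pre-treatment score the gap is near zero, (1 - r) x 0 = 0, and the two analyses would agree by construction. If the two differ, report both and interpret accordingly.
- Settle this before outcomes are compared between services.

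The cost is protocol wording and one extra analysis. No new data are needed, since both datasets already hold the score. Adding a matching variable will leave somewhat more cases unmatched, less so with propensity weighting than with exact matching.

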### **17.6 Health Economics**

We will assess the feasibility of comparing the cost of mental health care treatment for patients receiving treatment from mainstream mental health services compared to a SARC. Mental health resource use for patients attending traditional mental health services will be obtained from CRIS and costed using nationally published sources. The cost of the SARC will be calculated from the Kent SARC data, information collected from WP4 and the analysis conducted as part of WP3. We will conduct a cost-consequences analysis, reporting costs alongside outcomes for the two service types along with 95% confidence intervals to allow for evaluation of significant differences between the two service types. We will ensure the information reported is useful to policy makers and commissioners service planning and delivery through ongoing dialogue with key stakeholders.

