## 5. STUDY SUMMARY

Study Title	The Effectiveness of S exual Assault Referral Centres with regard to Mental Health and Substance Use: A National M ixed M ethods study
Internal ref. no. (or short title)	MiMoS study
Study Design	Realist Evaluation using Mixed Methods
Study Participants	Sexual Assault Referral Centre's (SARCs) and related service's staff, service users and stakeholders
Planned Study Period	01.06.2018 – 31.05.2021
Research Questions	
 
1. What programmes are identified in published and grey literature to inform how mental health and substance use can be best addressed in SARCs?
 
2. What models can be identified across the SARC services in terms of addressing mental health and substance use?
 
3. What is the prevalence and nature of mental health and substance use in people who attend SARCs?
 
4. What types of services are accessed by people with a range of needs following attendance at a SARC, and how satisfied are they with those services?
 
5. What are the barriers and facilitators to accessing the right support at the right time for people who have attended a SARC?
 
6. How do outcomes differ between a bespoke psychological therapies service at a SARC and mainstream mental health?
 

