### **12.4. Research objectives**

1. To undertake an evidence review of SARC provision for health outcomes (including mental health and substance use) (Work Package 1)
2. To identify what models of SARCs currently exist in England (Work Package 2)
3. To identify the mental health and substance use needs of attendees of SARCs (Work Package 3)
4. To identify what services are available, and to explore satisfaction with care, barriers to access and gaps in provision (Work Packages 2, 3 and 4)
5. To understand from the perspective of the workforce and their current practice, skills and training needs in terms of recognition of, and referral for, mental health and substance use issues (Work Package 4)
6. To obtain the survivor view on how they felt their emotional well-being was addressed by the SARC as well as external services (Work Package 4)

7. To compare health outcomes for people who experience sexual assault and access bespoke SARC psychological therapies provision compared to those who experience sexual assault and are in mainstream mental health services (Work Package 5)
8. To produce a range of lay and academic outputs that will aim to identify and share good practice in SARC services related to substance use and mental health in order to have an impact on care delivery (e.g. training materials, new methods of screening, local partnerships etc.) (all Work-Packages, and specifically Work Package 6).

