#### *Procedure*

#### *Datasets*

Data from this study will be collected from anonymised clinical datasets at a mainstream mental health service in London and a SARC service in Kent. The reason for selecting the mainstream mental health service in London is because it has the most well established anonymised health records system in England to date, providing data on a diverse sample of over 250,000 patients accessing mental health services, including substance misuse treatment, across four boroughs in London. The Kent SARC is also chosen because it is only one of the 47 SARCs in England to have an established comprehensive multi-agency psychological treatment pathway with specialist third-sector organizations. As part of this pathway, Kent SARC has established a central database system for the reporting of demographic and clinical data of service users, and since 2016 the service has been obtaining consent from service users to the sharing of their anonymised data for research purposes.

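### WP5 has one service per type, so the intervals in 17.6 can compare the Kent SARC with one London Trust but cannot show a significant difference between service types

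*Protocol*

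**What the plan says.** Section 17.2 (Datasets) takes the WP5 data from "a mainstream mental health service in London and a SARC service in Kent" and gives a reason for choosing each. On the SARC side it adds that "The Kent SARC provides the only bespoke psychological therapies service in partnership with the local mental health NHS Trust".

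The wording of the comparison varies by section:

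- Research question 6 (section 5) asks: "How do outcomes differ between a bespoke psychological therapies service at a SARC and mainstream mental health".
- Objective 7 (section 12.4) compares bespoke SARC therapy users, as a group, "compared to those who experience sexual assault and are in mainstream mental health services", in the plural.
- Section 17.5 examines change in CORE scores "following psychological treatment from a mainstream mental health service compared to a SARC", in the singular.
- Section 17.6 will report costs alongside outcomes with "95% confidence intervals to allow for evaluation of significant differences between the two service types". It aims the results at policy makers and commissioners.

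No section limits the conclusion to the two providers. Cases are to be matched on patient characteristics (section 17.2), and 17.5 adds stratification by gender and adjustment for differences between the cohorts.

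**The concern.** A significance statement about types needs an error term that includes how much services of the same type differ from one another, for example in staffing, local area, waiting times or discharge practice. One service per type gives no information on this. The interval then treats any ordinary difference between Kent and this Trust as evidence about the model of care, and adding patients strengthens that misreading. Matching and adjustment act on patient characteristics. They would leave the problem in place even if the two patient groups were perfectly balanced.

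What is at stake is the conclusion that commissioners take away. An interval that excludes zero would be read as showing that bespoke SARC therapy and mainstream care differ as models, when it can only show that these two providers differ.

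**Working it through.** **The protocol's own figure.** Section 17.3 estimates "around 300 women per year receiving psychological treatment" in the London records, "therefore approximately 900 cases for 2016 to 2019". 300 × 3 = 900, so the figure reproduces.

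**Degrees of freedom.** There are two services and two type means. 2 − 2 = 0 degrees of freedom remain for variation between services within type. This part needs no assumption.

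**Inputs for the illustration.**

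- London: about 900 cases (17.3), before matching.
- Kent: 16-20 referrals a month (17.3). Over an assumed 36 months, chosen to match 3 × 300, this is 16 × 36 = 576 to 20 × 36 = 720. These are referrals, so they are an upper bound on treated cases.
- Matched samples of 200 v 200 and 100 v 100: assumed, because the protocol gives no matched number.
- Between-service share of outcome variance (intraclass correlation, ICC): not in the protocol. Assumed range 0.005 to 0.02.
- Kent fixed: Kent is taken as the whole of its type, and the London Trust as one draw from mainstream services.

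**Formula.** With outcomes standardised to unit variance and no true difference between types:

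- patient-level variance of the difference: w = (1 − ICC)(1/n₁ + 1/n₂)
- between-service variance that the interval omits: b = ICC
- false rejection rate of a nominal 5% test = 2 × [1 − Φ(1.96 / √(1 + b/w))]

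**Worked case, ICC 0.01, 576 v 900.** w = 0.99 × (1/576 + 1/900) = 0.00282. b/w = 0.01/0.00282 = 3.55. √4.55 = 2.13. 1.96/2.13 = 0.92. Rate = 2 × [1 − Φ(0.92)] = 36%.

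**Results, Kent fixed.**

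| Kent v London | ICC 0.005 | ICC 0.01 | ICC 0.02 |
|---|---|---|---|
| 576 v 900 | 24% | 36% | 49% |
| 720 v 900 | 26% | 38% | 52% |
| 200 v 200 | 11% | 17% | 26% |
| 100 v 100 | 8% | 11% | 17% |

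At ICC 0.001 the rate is 9-10% at the unmatched counts and about 6% at 100 v 100 or 200 v 200. At ICC 0 it is 5%. A simulation of 20,000 datasets at 576 v 900 with Kent fixed gave 5.2% at ICC 0 and 35.6% at ICC 0.01, in line with the formula.

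**The narrower question.** If the conclusion is worded as Kent v this Trust, the between-service term is no longer omitted error, and the sampling error returns to the nominal 5%.

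**The case against.** **The protocol mostly speaks of single services.** Section 17.5 and the WP5 aim in 17.1 use the singular, and both providers are named and justified. Significance about types is claimed only in 17.6. This stands: a reader might infer that the main outcome analysis in 17.5 makes the same claim, and it does not. Still, 17.6 covers costs alongside outcomes, objective 7 generalises to mainstream services, and nothing limits the conclusion.

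**The section is about cost and feasibility.** 17.6 opens by assessing whether costs can be compared at all, and the SARC cost also uses WP3 and WP4 information, which comes from other sites as well. This weakens the point for costs. It does not reach outcomes, which come only from the two datasets.

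**Kent is the only service of its kind.** A reader might treat both services as random draws and infer a larger error: by the same formula with b = 2 × ICC, 36-64% at the unmatched counts for ICC 0.005-0.02. The protocol's description of Kent does not support a population of such services, so the Kent-fixed figures are the ones to use. Fixing Kent lowers the inflation without removing it, since one Trust still stands for mainstream care.

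**The ICC and sample sizes are not the protocol's.** This also stands. The ICC is assumed, 900 and 576-720 are counts before matching, and the Kent count is of referrals. A flat statement that the test rejects far more often than 5% is not supported: with small matched groups and a small ICC, the excess is slight.

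**Conclusion.** The significance wording in 17.6 is wrong as written. With one service per type, the planned intervals reflect patient sampling within the Kent SARC and one London Trust. They cannot support a significance claim about service types, whatever matching or adjustment is applied. That structural conclusion is certain. Because Kent is described as unique, the unsupported step is mainly from one Trust to mainstream services in general.

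The size is illustrative. With Kent fixed and an assumed ICC of 0.005-0.02, the false rejection rate runs from 24-52% at the unmatched counts down to 8-17% with 100 matched cases per group. It exceeds 5% for any ICC above zero. The point applies most clearly to outcomes and less to costs.

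**What to change.** 1. In 17.6, refer to differences between the Kent SARC pathway and the London Trust, in place of significant differences between service types.
2. In 17.5 and 17.6, state that the intervals cover patient sampling within these two services and do not support a significance claim about SARC v mainstream care in general.
3. Align objective 7 (sections 5 and 12.4) with that scope.

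This needs no new data or sites. The downside is a narrower claim.

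A random effect for units within the two services (the Kent providers; boroughs or service levels in London) is not a substitute, because it cannot remove an effect shared by all Kent units or all units of the Trust. In a simulation with 3 Kent units and an assumed 8 London units, a t-test on the 11 unit means rejects about 4% of the time when no such shared effect exists. With service-level and unit-level ICC both at 0.01 it rejects 25% of the time, or 15% with Kent fixed. The units also differ systematically in treatment and severity, so they are not interchangeable replicates.
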